7.7.3 Response to Hypoglycemia

- Participants in all study arms are encouraged to check their BG for any symptoms of hypoglycemia and in response to any CGM alarms.
- During the usual care arm, subjects are encouraged to treat hypoglycemia according their usual practice or according to the rule of 15s: take 15 grams of rapid acting carbohydrate and recheck in 15 minutes, then repeat as needed.
- While using the iLet bionic pancreas, participants will be instructed to consider using less

carbohydrate to treat or prevent hypoglycemia, since due to insulin suspension 5-10 grams is often sufficient and is less likely to lead to hyperglycemia.

- If a participant experiences a seizure or unconsciousness associated with hypoglycemia the PI will make a determination regarding whether it will be safe to allow them to continue in the study. A participant using the iLet bionic pancreas when they experienced severe hypoglycemia will suspend use of the device until a determination is made about the safety of having them continue.
 - If the PI concludes that the event is explainable and unlikely to recur, the participant will be allowed to continue to use the system. Further study participation of an individual participant will be discontinued if they experience more than one episode of DKA requiring hospitalization, more than one episode of seizure or unconsciousness associated with hypoglycemia, or one of each.

7.7.4 Response to Hyperglycemia

- Participants in the usual care arm will manage their hyperglycemia in their usual way. They will be taught to contact study staff at any time for assistance as needed.
- Participants in the bionic pancreas arm will be required to check ketones whenever CGM glucose is > 300 mg/dl for 90 minutes, > 400 mg/dl once, or with symptoms of diabetic ketoacidosis.
- Participants will be instructed to check their insulin infusion site and their pump or bionic pancreas for normal operation any time they experience hyperglycemia. If there is any suspicion of insulin infusion set malfunction, the site should be replaced. Participants will be taught how to recognize if an infusion set might be failing and need replacement, including recognizing that the sensor glucose is rising or not falling despite sufficient insulin being pumped by the iLet, that the sensor glucose is >300 mg/dl for more than 90 minutes, or that the sensor glucose is >400 mg/dl.
 - It will be emphasized in participant training to have a low threshold of suspicion to changing out the infusion set, and emphasizing that “when in doubt, change it out.” Participants will be told that sufficient supplies are available so that they should not hesitate to change out the infusion set if they have any doubt that it is working well.
- Participants may contact a study provider (MD or NP) for advice at any time, and may contact the troubleshooting support team, as they wish. During the iLet bionic pancreas arm, they will be assisted in checking the bionic pancreas for any malfunction and correcting and problems that are found.
 - If no correctable fault is found, but there is doubt regarding the correct function of the bionic pancreas system, an entirely new backup bionic pancreas system may be brought to the participant’s location by study staff.
- Detailed information about the hyperglycemia treatment plan can be found in Appendix C.
- Unlike in patients with type 1 diabetes, diabetic ketoacidosis (DKA) is very rare in patients with CFRD due to underlying residual beta cell function. However, in the unlikely case that a participant experiences diabetic ketoacidosis requiring hospitalization, the PI will make a determination regarding whether it will be safe to allow them to continue in the study. A participant using the bionic pancreas when they experienced diabetic ketoacidosis will suspend use of the device until a determination is made about the safety of having them continue.
 - If the PI concludes that the event is explainable and unlikely to recur, the participant will be allowed to continue to use the system. Further study participation of an individual participant will be discontinued if they experience more than one episode of DKA requiring hospitalization, more than one episode of seizure or unconsciousness associated with hypoglycemia, or one of each.

7.7.5 Response to Other Medical Needs

If the participant experiences any non-emergent medical concerns outside the scope of diabetes care, he or she will see their personal physician. If the participant experiences urgent or emergent medical concerns outside the scope of diabetes care and their primary care physicians, they should visit a walk-in clinic or emergency room, or if necessary, call 911.

7.7.6 Monitoring of Bionic Pancreas Performance

Beta Bionics customer support will be readily available by phone for consultation at all times during the course of the study.

7.7.7 Supervision by Study Staff

A study provider (MD or NP) will be on call at all times during the course of each experiment. All device training will be performed by study personnel with the appropriate training and experience, such as a Certified Diabetes Educator, Physician's Assistant, Registered Nurse, Nurse Practitioner, or Physician.

Study staff will emphasize to participants that they must carefully follow study policies, including the ketone action plan, for their safety. They will be instructed to call study staff whenever indicated or needed, regardless of the hour.

Study staff will be trained that if a participant calls and is found to be in Zone 2 of the Ketone Action Plan or has a plasma glucose <54 mg/dl, they must speak directly to a Certified Diabetes Educator, Physician's Assistant, Registered Nurse, Nurse Practitioner, or Physician. If a participant calls and is in Zone 3 of the Ketone Action Plan or has had a severe hypoglycemic event requiring assistance from another person, either the participant or someone with them and assisting them must speak directly to a Physician's Assistant, Registered Nurse, Nurse Practitioner, or Physician *and the Site PI must be informed*.

Whenever a participant contacts with hyperglycemia and is in Zone 2 or Zone 3 of the ketone action plan or has a glucose <54 mg/dl, study staff with the appropriate training and experience (Certified Diabetes Educator, Physician's Assistant, Registered Nurse, Nurse Practitioner, or Physician) must attempt to ascertain whether the participant has the capacity to care adequately for themselves with guidance. If based on their experience and judgement they believe the participant may not be adequately able to care for themselves without assistance, then they must either directly communicate with someone on the scene who they judge to have that capacity, or call 911, or both.

If based on their experience and judgment study staff believes that the participant needs emergency care, they should recommend to the participant that they go to an emergency department. Study staff should determine which emergency department the participant will be taken to and follow up within 15 minutes of the expected arrival time to make sure they have arrived. If the study staff calls 911 they should remain on the telephone with the participant until the ambulance arrives and speak to the Emergency Medical Technicians to provide history and determine where the participant will be taken.

Whenever a participant is sent to the emergency department, study staff must confirm that the participant has arrived at ED within an hour, and study staff member should speak with a member of the medical staff at the emergency department to confirm arrival and provide information about the reason for referral to the ED.

If a participant cannot be reached and there is concern for their wellbeing (e.g. if their Clarity data shows

hypoglycemia or severe hyperglycemia) then study staff should attempt to reach close contacts. If no contacts are available or their contacts do not succeed in reaching them quickly, then 911 should be called and a well-being check should be requested. Study staff must follow up on and document the results of the well-being check.

8. Biostatistical Analysis

8.1 Data Collected During Study Arms:

- CGM glucose (CGM glucose) every five minutes from the Dexcom CGM
- CGM data sufficiency (percentage of possible CGM values captured)
- All fingerstick BG measurements taken by the participant (meter download)
- Information collected from the daily email survey and phone calls including hypoglycemia, carbohydrate interventions, any other adverse events, any unscheduled infusion set changes or Dexcom CGM sensor changes.
- Insulin total daily dose (from the bionic pancreas, insulin pump download, or InPen)
- Timing of meal announcements and size of meals announced (in the bionic pancreas arm)
- Data from a questionnaire about attitudes and expectations regarding the bionic pancreas at baseline and on day 14 of each arm.
- Time under bionic pancreas control with CGM data in bionic pancreas arm
- Time under bionic pancreas control without CGM data in bionic pancreas arm
- Percent of time not under bionic pancreas control during the bionic pancreas arms
- List of technical faults associated with the bionic pancreas including cause and resolution
- Body weight after each arm

8.2 Outcomes

Study endpoints will be calculated for days 3 – 14 so that any long-acting insulin on board has time to clear and therefore does not affect study outcomes. Adverse events will be reported for the entire study period.

The primary analysis of the designated endpoints will be calculated on an intention-to-treat basis, including data from periods when the bionic pancreas was not in use, if available (Dexcom CGM data may not be available in some failure modes). In cases where an arm was not completed, we will use the available data from that arm in the data analysis. We will calculate percentages, means and standard deviations or medians and interquartile ranges as appropriate. We will use paired t-test for comparison of means for normally distributed data and the Wilcoxon signed rank test for non-normally distributed data. We may, in exploratory analyses, also stratify participants for secondary analyses of the pre-specified endpoints by participant characteristics including: sex, age, use of CGM in usual care, baseline A1c, usual care insulin total daily dose, body mass index, FEV1, CFTR genotype, and/or number of CF exacerbations in the preceding year. Given the potential difference in glucose variability, participants under the age 18 will also be analyzed separately from the adult cohort.

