3.2 Number of Participants

It is expected that 20 adult participants ≥ 18 years and up to 10 pediatric participants 10 – 17 years will complete the main study. We expect that the experiments and analysis can be accomplished over a period of 1 to 2 years. Up to 60 participants will be enrolled. The bound is based on the expectation that some volunteers will be excluded after the screening visit and the possibility that some experiments may have to be discontinued before completion (due to, for instance, intercurrent illness or participant withdrawal).

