4.1 Inclusion Criteria

- Age \geq 10 years and have had a diagnosis of CFRD managed using either an insulin pump or multiple daily injections (MDI).
 - If < 18 years of age, they must have someone over 18 years of age who lives with them (adult guardian) and has knowledge of hypoglycemia treatment
- Diabetes managed using the same regimen (either pump or MDI, with or without CGM) for ≥ 1 month prior to screening, with no plans to change regimen before or during the study
- Mean CGM glucose ≥ 125 mg/dl as determined by the participant's personal CGM 30-day download if CGM is used as part of their usual care. If the participant does not use CGM, hemoglobin A1c $\geq 6\%$ within the last 6-months from available medical records will be required.
 - Study participants who are transplant recipients must have a hemoglobin A1c $< 9\%$
- Minimum insulin requirement of ≥ 0.1 u/kg/day. To ensure that participants with a wide range of insulin requirements are included, participants whose insulin requirement is < 0.3 u/kg/day will be limited to approximately $\sim 1/3$ of the enrolled ≥ 18 year old adult cohort.
- Willing to wear iLet infusion sets and one Dexcom CGM sensor and change sets at least every 3 days in the iLet arm
- Assent will be obtained for patients < 18 of age
- The Investigator believes the participant can safely use the iLet and will follow the protocol

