iLet Infusion Set: While in the iLet arm of the study, participants will be provided with iLet infusion sets for the system. Study staff will work with the participants to ensure they are properly inserting the infusion set and will help them troubleshoot if problems related to the infusion set arise. Participants will be instructed to replace their infusion set as needed when it fails (or is suspected of failing) or falls out, or every 3 days.

iLet Ready-to-Fill Insulin Cartridges: Participants in the iLet arm will be provided with iLet Ready-To-Fill insulin cartridges for the system and a syringe for transferring insulin from a vial to the cartridge. Study staff will work with the participants to ensure they are comfortable with the fill process. Participants will be instructed to replace their insulin cartridge as needed or a minimum of every 3 days.

Ascensia Diabetes Care Contour Next One Glucose Meter: The Contour Next One glucometer is FDA approved and commercially available. Blood glucose measurements for Dexcom CGM calibrations and other required BG measurements will be obtained via finger stick with the Contour Next One in both study arms.

Abbott Precision Xtra Ketone Meter: The Precision Xtra is FDA approved and commercially available. Blood ketone measurements for hyperglycemia management will be obtained via finger stick with the Precision Xtra ketone meter in the bionic pancreas arm.

7. Experimental Procedures and Data Collection

7.1 Randomization of Study Visit Order:

Once the participant has been enrolled and eligibility has been established, participants will be randomized to one of the possible 2 visit-order schedules. We will schedule in-clinic visits so that infectious disease isolation protocols for these participants are not breached.

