- The participant will be asked to demonstrate their competency by placing at least one practice infusion site and one site in themselves and “teach back” to confirm that they adequately understand when to replace a set. Study staff will be trained that participants who have not previously used an insulin pump or who have not previously used the study infusion set may need additional time for training on pump-related tasks, such as placement of infusion sets and how to recognize when an infusion set needs to be replaced.
- Study start visits for participants who may need more assistance with the iLet and the infusion set, and/or participants who live alone should be scheduled early in the day so that there is sufficient time before bedtime to recognize if the first infusion set is not performing well. Study staff may follow up with participants that need additional support before the end of the first day to confirm everything is working and the participant is comfortable.

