8.3 Power Analysis

The sample size was selected to detect superiority of the iLet bionic pancreas relative to the comparator group of usual diabetes care based on the primary outcome, percentage time of glucose in target range 70 – 180 mg/dl. The mean and SD of the CGM time in target range for the usual care group was derived from unpublished CGM data in patients with CFRD who wore a blinded CGM for 14 – 28 days. Based on the inclusion criteria of mean glucose ≥ 125 mg/dl (which equates to an expected A1c $> 6\%$), patients had a time in target range of $50 \pm 18\%$ in their usual care. The iLet bionic pancreas is expected to achieve a time in range of $70 \pm 12\%$ based on data from patients in type 1 diabetes. Nine subjects would be required in order to detect a difference between arms using a paired t-test for a power of 80% at an alpha of 5% assuming a correlation pre- and post-treatment of 0.3. We increased the sample size to up to 30 subjects (20 adult subjects and up to 10 pediatric subjects) in order to account for the potential increased variability in glycemic control in response to the bionic pancreas in patients with CFRD, to increase the exposure to the treatment to gather data on safety, and to increase power for detecting differences in secondary outcomes.

9. Risks and Discomforts

Participants may experience mild discomfort associated with the insertion of the infusion sets and the Dexcom sensor. The risk of discomfort due to insertion of infusion sets and sensors may be greater than in their lives outside the trial because it may be more infusion sets and sensors than are used in their usual care.

There is a risk of feeling light-headed from coughing to produce a sputum sample.

There is a risk of hypoglycemia. In the Usual Care arm, this risk is expected to be of the same nature and magnitude as during the participants' lives outside of the trial. In the bionic pancreas arm, this risk is expected to be the same or lower than the risk during the participants' lives outside of the trial based on data from earlier trials. All of the previous studies, albeit in type 1 and type 2 diabetes, have shown that hypoglycemia is similar in the insulin-only configuration of the bionic pancreas when compared with usual care. Based on our experience, we believe that the risk of hypoglycemia will be the same for those with

CFRD.

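### The crossover's paired tests ignore period and no balancing of the two orders is stated; blocked orders and a period-adjusted estimate would be a cheap improvement, not the repair of an error

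*Combined protocol and SAP*

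**What the plan says.** Section 7.1 states that "participants will be randomized to one of the possible 2 visit-order schedules". It gives no ratio, blocking, stratification or list method. Section 8.2 gives the comparison: "We will use paired t-test for comparison of means for normally distributed data and the Wilcoxon signed rank test for non-normally distributed data". The exploratory stratification factors in 8.2 do not include order, and no period or sequence term appears elsewhere. Section 8.2 adds that "participants under the age 18 will also be analyzed separately from the adult cohort". Section 8.3 sizes the trial on the same paired t-test, "assuming a correlation pre- and post-treatment of 0.3". Section 3.2 allows that "some experiments may have to be discontinued before completion", so even a balanced list could end with unequal orders.

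**The concern.** A period effect is any change from the first arm to the second that would occur under either treatment, such as a change in behaviour under observation. It enters the iLet minus usual-care difference with opposite sign in the two orders. With equal orders it cancels from the mean but widens the spread of the differences. With unequal orders part of it stays in the estimate. At stake are the size of the reported difference in time in range and its interval (8.2 names none), and the separate under-18 analysis of up to 10 participants, where a chance imbalance is proportionally larger.

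**Working it through.** **Inputs.** From Section 8.3: SDs 18 and 12, correlation 0.3, means 50% and 70% (a 20-point effect), paired t-test, 80% power, alpha 5%, nine participants required, 20 adults and up to 10 under-18s planned. Assumed, because the documents are silent: additive period effects of 5 or 10 points, normal differences and, for split probabilities only, simple 1:1 randomization. Rejection rates with a non-zero period effect come from simulation with at least 100,000 trials per setting.

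**1. The plan's own figure.** SD of the difference = √(18² + 12² − 2×0.3×18×12) = √338.4 = 18.4. Two-sided paired t power for 20 points is 75.1% at n=8 and 81.4% at n=9. The stated nine is reproduced.

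**2. Shift.** Let π be period 2 minus period 1. The mean difference is δ+π when usual care comes first and δ−π when the iLet comes first. The pooled mean is therefore δ + π(n1−n2)/n, where n1 is the usual-care-first group. At 14:6 and π=5: 5×8/20 = 2.0.

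**3. Averaged over simple randomization.** The expected value of n1−n2 is zero, so the estimate is unbiased. Paired type I error is about 5% at n=10, 20 and 30 for period effects of 0, 5 and 10.

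**4. Given the split, n=20.**

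| Split | Probability | Shift (π=5 / 10) | Paired type I error (5 / 10) | Adjusted |
|---|---|---|---|---|
| 10:10 | 17.6% | 0 / 0 | 4.2–4.3% / 2.6% | about 5% |
| 12:8 | 50% (this or worse) | 1.0 / 2.0 | 4.9% / 4.3% | about 5% |
| 14:6 | 12% (this or worse) | 2.0 / 4.0 | 6.6% / about 10.4% | about 5% |

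**5. Equal orders.** At 10:10, power for an assumed 10-point benefit is 61% (π=5) or 52% (π=10) with the paired test, against 63% adjusted. Blocking alone removes the shift but not this loss.

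**6. Cost of adjusting.** The adjusted standard error is (18.4/2)×√(1/n1+1/n2): 4.11 at 10:10, 4.20 at 12:8, 4.31 at 13:7 and 4.49 at 14:6. The paired value is 18.4/√20 = 4.11. With no period effect, power for 10 points is 63.6% paired, and adjusted is 63.3% at 10:10, 61.6% at 12:8 and 55.9% at 14:6.

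Paired mean squared error is [π(n1−n2)/n]² + 18.4²/n; adjusted is its squared standard error. Setting them equal at 14:6: √(4.49²−4.11²)/0.4 ≈ 4.5 points. The same step gives about 4.2 at 12:8 and 4.3 at 13:7. Below those period effects the paired estimate has the smaller mean squared error.

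**7. The planned 20-point effect, n=20.** Adjusted power is 99.6% (10:10), 99.4% (12:8) and 98.8% (14:6). Paired power at 10:10 is 99% or more for period effects up to 10. If a 10-point period effect works against the iLet, paired power is 97% at 12:8 and 93% at 14:6.

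**8. Under-18, n=10.** At 7:3 the shift is 2.0 or 4.0 points. With no period effect, power for 20 points is 86% paired, and adjusted is 85% at 5:5 and 79% at 7:3. Adjustment lowers mean squared error only above about 5.9 (6:4) or 6.3 (7:3) points.

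**The case against.** The best defence is that nothing here is wrong as written. The order is randomized, so the paired test is valid on average, it is the test the sample size assumed, and Section 1.4 describes the pilot's primary purpose as feasibility. All of that stands.

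The period effect is also assumed, and several features should limit it. Section 4.1 requires a stable regimen, "with no plans to change regimen before or during the study". Sections 7.2 and 7.4 check iLet skills at the start of the iLet arm in either order: "The participant will be asked to demonstrate their competency by placing at least one practice infusion site". Days 1–2 are dropped "so that any long-acting insulin on board has time to clear". A 10-point period effect would be half the planned treatment effect. This also stands, and it is why the sizes above are a range and not a prediction.

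Imbalance is partly assumed too. Silence in Section 7.1 does not establish simple randomization. Sections 7.7 and 8.2 help to keep pairs: partial-arm data are generally used, those who stop the device are asked to continue CGM and visits, and a hospitalized participant may restart the arm. These measures reduce the risk of unequal orders among those analysed but do not remove it.

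A reader might infer that adjustment always sharpens the estimate. Step 6 shows otherwise: with unequal orders and a small period effect, it is less precise.

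**Conclusion.** This is a cheap improvement worth making, not an error. The gain is protection against bias given the split obtained, plus recovered precision when orders are equal and a period effect exists. At n=20 the shift is 1.0 or 2.0 points at 12:8 and 2.0 or 4.0 at 14:6, for assumed additive effects of 5 or 10 points.

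Two stronger readings are not supported. One is that the paired test is biased or invalid; randomization of order rules that out on average, and no document gives evidence of a period effect. The other is that the superiority conclusion is in doubt; for the planned 20-point effect it is unlikely to change. The opposite reassurance, that power is untouched whatever the split, is also too strong, given the 97% and 93% in step 7.

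**What to change.** 1. If randomization is still open, balance the order list with concealed permuted blocks of varying size, by age group. If it has closed, item 2 can still be adopted.
2. For primary time in range (days 3–14), take each participant's iLet minus usual-care difference, average it within each order, and estimate the treatment effect as the mean of the two order means. Use the pooled within-order variance and n−2 degrees of freedom, and report the estimate with a 95% confidence interval. With complete pairs this equals a linear model with participant, treatment and period terms.
3. Keep the paired t-test as a sensitivity analysis. In the under-18 subset report both estimates.
4. For skewed outcomes, a rank-sum test comparing period 1 minus period 2 differences between the orders may be added as a period-robust sensitivity test. Do not quote half the between-order shift as the effect for time below 54 mg/dl: Section 1.3 reports pilot arm values of 0.2–0.5%, and an additive shift is doubtful so near zero.
5. State that the term does not address carryover or a treatment-by-period interaction, such as familiarity that helps mainly the iLet when it comes second.

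The cost is SAP wording, a few lines of code, one degree of freedom, and a larger standard error when orders are unequal. Blocking limits that last cost, so items 1 and 2 belong together where both are possible.
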